| Days 9 and 10 (Study days 16 and 17)      | 0.36         | 0.72         | 0.72         |
| Days 11-40
(Study days 18-40)          | 0.72         | 0.72         | 0.72         |

Trained study personnel will evaluate heart rate, orthostatic blood pressure, pre-syncope and syncope signs and symptoms at all study visits during the titration period. If the study participant does not have bradycardia, orthostatic hypotension, or pre-syncope or syncope signs or symptoms as defined above, the dose of Lofexidine will be increased according to the titration schedule (**Table 2**). If bradycardia, orthostatic hypotension, or signs/symptoms of pre-syncope or syncope are identified at any point, the dose of Lofexidine will be lowered to the prior tolerated Lofexidine dose and the participant will remain at that dose for the duration of the study. At the beginning of the study, participants will be given a rescue pack of 36 tablets in case visits are missed. This will cover 3 days at the full dose.

The medical provider will inform the participant, verbally and with a take-home hand-out, of common side effects of lofexidine (dizziness, somnolence, dry mouth) and precautions to minimize risks associated with blood pressure (BP) decreases (hydration, standing up slowly). Participants will attend study visits three times a week during the induction period and throughout the study during which a UDS will be collected. The MUSC Investigational Drug Service will be responsible for randomization, will keep a record of the blind and will be available should unblinding be required. In the event that WorldMeds is unable to supply matching placebo. lofexidine tablets (supplied by US WorldMeds) will be encapsulated along with matching placebo capsules by Pitt Street Pharmacy, a specialty compounding pharmacy. Randomization will be stratified on presence/absence of other substance use as well as the presence/absence of significant childhood trauma (ACE>4).

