Statistics and Data Analysis (complete statistical/data analysis plan in Biostatistics Resource Core): Aim 1: Using a human laboratory paradigm, determine the impact of lofexidine on stress and drug cueinduced craving in women and men with OUDs: The primary study outcome of interest in Aim 1 is the differential craving, stress and anxiety response to a human laboratory paradigms containing both a stressor (TSST) and an opioid specific cue between participants randomized to lofexidine and placebo in addition to buprenorphine/methadone maintenance. Hypothesis 1: Lofexidine will attenuate drug craving and subjective stress response to a stress task in opioid-dependent individuals compared to individuals receiving placebo. Hypothesis 2: Lofexidine will attenuate drug craving and subjective stress response to a drug-related cue in opioid-dependent individuals. Hypothesis 3: The ameliorative effects of lofexidine on stress and cue-reactivity will be more pronounced in females than male subjects. To assess the hypothesis that lofexidine will attenuate drug craving and subjective stress response to the stressor and the opioid-related cue task, multilevel longitudinal GLMMs will be developed using all post-stressor and post-cue data. Initial models will control for study design aspects such as order (stressor or cue first), treatment assignment, and baseline craving and stress (task level). Covariate adjusted models will additionally include baseline characteristics determined to be correlated with study outcomes or those determined to be significant effect modifiers. To examine the differential effects of lofexidine on stress and cue-reactivity across female and male subjects, the models will have additional parameters added to include an indicator of participant gender and the interaction between gender and randomized treatment assignment. Relevant interactions will be assessed in all models. Least square means and associated standard errors will be assessed to compare craving and subjective stress response between treatment assignments at all time points.

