Aim 2: To evaluate the impact of lofexidine on opioid craving and subjective experience of daily stressors in men and women with OUDs: The primary measures of interest for Aim 2 are craving and stress ratings in response to stress-related cues using *Cue Reactivity Ecological Momentary Assessment* (CREMA) as well as subjective experiences of daily life stressors Hypothesis 1: Lofexidine will decrease craving and decrease the subjective experience of daily stressors in opioid-dependent men and women. Exploratory Hypothesis 2: Lofexidine will be more efficacious in decreasing stress-related craving in opioid-dependent women as compared to men. To assess this hypothesis a multilevel generalized linear mixed effects models with repeated measures (GLMMs) will be developed using CREMA session response data from the 5-week period during study medication administration. Pre-cue stress and craving rating will be centered and used as a time varying covariate in all analysis. Additionally, CREMA cue response data during the 7 day baseline assessment period will be used as a time naïve covariate in all analyses. Least squares means and associated standard errors will be used for post-hoc comparisons of craving and stress response between women and men over time. Models developed to address hypothesis 2 will be utilized to examine the impact of gender on opioid use and stress-related craving during study treatment. All other relevant interactions will be assessed in all models.

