Exploratory Aim 3: To evaluate the impact of lofexidine on illicit drug use in men and women with OUDs: Daily use data will be collected through morning reports via EMA and verified by urine drug screens (3 times weekly). Hypothesis 1: Lofexidine will increase the number of consecutive days abstinent as compared to placebo. Hypothesis 2: Lofexidine will be more efficacious in increasing consecutive days abstinent in women as compared to men. Time to relapse will be calculated as the days between the start of study medication (following titration; day 14) and the first day of lapse to opioid use or the laboratory stress induction day (day 40). Additionally, daily use data will be examined to determine the maximum number of consecutive days abstinent during follow up. Kaplan-Meier estimates and log-rank tests will be used to assess initial relationships between study treatment assignment and relapse while Cox proportional hazards models will be developed to assess the differential time to return to use across gender (using and appropriate interaction term). A significant interaction indicates that treatment may impact return to use time differently in women and men. Proportionality of hazards will be assessed using log-log plots and log-time interactions.

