## Power and Sample Size (complete sample size justification available in Biostatistics Resource Core):

The current study is powered on the primary Aims 1 and 2. In the proposed study, response to a laboratory stressor, CREMA cue response and daily use data will be tested using GLMMs (assuming a Gaussian distribution) and the study will be powered to sufficiently address the least of the study treatment effect sizes determined to be clinically meaningful for the study hypothesis. Aim 1: Sinha and colleagues (Sinha, et al 2007), in a small pilot sample, demonstrated that lofexiding in combination with naltrexone attenuated craving and anger in response to laboratory drug and stress cues as compared to naltrexone alone. Results indicate a larger change in opioid craving scores in response to drug-related and stress cues occurs in placebo participants than lofexidine treated participants [Drug related cue response  $\Delta$ =2.2; SDP=2.6; between group Cohen's d=0.85, p<0.05 and stress cues response  $\Delta$ =2.1; SDP=2.4; between group Cohen's d=0.88, p<0.05]. Moreover, Fox and colleagues (2014) conducted a trial of quanfacine in cocaine-dependent individuals and noted stress and craving response to stress and drug-related imagery. They noted significant gender differences across treatment assignment for craving and stress response to drug-related imagery [Craving  $\Delta$ =3.0; SDP=3.8; Treatment x Sex Intx Cohen's d=0.79, p<0.05; Negative Emotion  $\Delta=3.0$ ; SDP=2.9; Treatment x Sex Intx Cohen's d=1.0, p<0.05]. Sample sizes in both the Sinha and Fox studies were somewhat small. Smaller but still clinically relevant effect sizes in an adequately powered study are anticipated. Therefore, a 20% reduction in craving and stress response from the previous studies is anticipated in the current design (Cohen's d=0.64 for the sex x treatment interaction on craving response). Aim 2: Kowalczyk and colleagues (2015), showed that daily life craving reports as measured by EMA were significantly reduced in opioid using participants randomized to clonidine as compared to placebo [6.3% (95% CI=5.6-7.1) vs. 11.8% (10.9-13.0); between group Cohen's *d*=1.6]. To assess the least of the differences anticipated in project 2, a sample size of 39 participants randomized to each female and males across active lofexidine and placebo groups would provide 80% power with a type 1 error rate of 5% to detect the treatment x sex interaction in craving and stress response to laboratory drug based cues (total n=156; 78 per group). We anticipate 25% attrition between randomization and the end of the 5-week active treatment period. Thus, inflating the necessary sample size to 68 participants randomized per treatment group with a total of n=136 randomized participants will provide adequate power.

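### Name both randomisation strata in the Aim 1 and Aim 2 models and say which Aim 1 model is primary: a nearly free improvement

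*Combined protocol and SAP*

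**What the plan says.** Randomisation (C.2.c.5, Phase 1, item d): "Randomization will be stratified on presence/absence of other substance use as well as the presence/absence of significant childhood trauma (ACE>4". That makes four strata; gender is not one of them.

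Analysis (C.2.d):

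- **Aim 1, initial model.** "Initial models will control for study design aspects such as order (stressor or cue first), treatment assignment, and baseline craving and stress". The list is introduced by open wording, and neither stratum is in it.
- **Aim 1, covariate-adjusted model.** "Covariate adjusted models will additionally include baseline characteristics determined to be correlated with study outcomes or those determined to be significant effect modifiers". Gender and its interaction with treatment are then added to the models, without saying which of the two. Neither model is called primary.
- **Aim 2.** "Pre-cue stress and craving rating will be centered and used as a time varying covariate in all analysis". Cue response from the baseline week is the other named covariate. No covariate-adjusted version is mentioned.
- **Exploratory Aim 3.** "Kaplan-Meier estimates and log-rank tests will be used to assess initial relationships between study treatment assignment and relapse". A Cox model with a gender interaction follows. Neither analysis is said to be stratified or adjusted by the randomisation factors.

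The heading of this part refers the reader elsewhere: "complete statistical/data analysis plan in Biostatistics Resource Core". That plan is not among the documents.

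**The concern.** Two separate matters arise.

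First, stratified allocation balances the arms on the strata, so the treatment difference varies less from trial to trial than an analysis ignoring the strata assumes. If the strata are prognostic, that analysis uses too large a standard error. The treatment test then rejects too seldom under the null, and part of the benefit of stratifying is lost. The treatment-by-gender test keeps its level, because gender is not a stratum, but it carries residual variance that could have been removed. C.2.c.3 says the childhood-adversity data are meant to help assess the effect of early trauma on opioid use, so the sponsor evidently thinks this factor may matter.

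Second, Aim 1 has two unranked models, and the covariates of one depend on the outcome. The same hypothesis could be declared from either, including the gender interaction on which the trial is sized.

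**Working it through.** **Inputs from Power and Sample Size.** 136 are randomised, 68 per arm. "We anticipate 25% attrition between randomization and the end of the 5-week active treatment period", so 136 × 0.75 = 102 are analysed. Effects are shrunk: "a 20% reduction in craving and stress response from the previous studies is anticipated in the current design". The treatment effect on cue-induced craving becomes 0.85 × 0.8 = 0.68 SD. The plan states 0.64 for the interaction.

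**The plan's own figure.** 2 × (1.96 + 0.8416)² / 0.64² = 38.3, so 39 per group (power 0.807). This reproduces the stated 39, but as a comparison of two groups. The present point does not depend on it.

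**Assumptions not in the documents.** The strata's share of response variance beyond the baseline ratings (R²) is taken as 0, 0.05, 0.10, 0.15 or 0.30, split equally between the two. Stratum prevalences are 50% and 40%, with permuted blocks of 4. Dropout is random, tests are two-sided at 5%, and each person contributes one mean response with SD 1. The 0.64 is read as the difference between the two sexes' treatment effects.

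**Formulas (perfect balance, normal approximation).**

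- Treatment type I error without strata = 2 × [1 − Φ(1.96/√(1−R²))]. At R² = 0.10 this is 2 × [1 − Φ(2.066)] = 3.9%.
- Standard error of treatment = √(4/102) = 0.198, and of the interaction = 4/√102 = 0.396.
- Interaction power without strata = Φ(0.64/0.396 − 1.96) = 36.5%. With strata at R² = 0.10, the standard error is multiplied by √0.90 and power is 39.9%.

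**Simulation (50,000 runs per cell; without / with strata, %).** Dropout disturbs the balance a little, so the test is somewhat less conservative than the formula says.

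| R² | Treatment type I error | Treatment power, 0.68 SD | Interaction power, 0.64 SD |
|---|---|---|---|
| 0 | 4.92 / 4.92 | 92.5 / 92.4 | 35.9 / 35.4 |
| 0.05 | 4.53 / 4.93 | 92.8 / 93.6 | 35.7 / 36.6 |
| 0.10 | 4.24 / 5.00 | 93.2 / 94.8 | 35.3 / 37.9 |
| 0.15 | 3.68 / 4.93 | 93.7 / 95.7 | 35.4 / 39.9 |
| 0.30 | 2.75 / 5.15 | 94.6 / 98.1 | 35.1 / 46.5 |

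Interaction type I error is 4.8 to 5.1% either way. If the strata are irrelevant (R² = 0), including them costs 0.1 point for treatment and 0.5 for the interaction.

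**Does the Aim 1 covariate-adjusted model already cover this?** Suppose a stratum enters when its correlation with the outcome has p < 0.05 (assumed; the plan gives no rule). Power in % for initial / screened / both strata always included (8,000 runs per cell):

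| R² | Treatment | Interaction |
|---|---|---|
| 0.05 | 92.6 / 93.0 / 93.2 | 34.6 / 34.5 / 35.3 |
| 0.10 | 93.4 / 94.9 / 95.1 | 35.3 / 36.4 / 37.5 |
| 0.15 | 93.4 / 95.1 / 95.3 | 35.6 / 39.5 / 40.3 |
| 0.30 | 94.6 / 98.1 / 98.1 | 35.4 / 46.9 / 47.1 |

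The screen tends to drop strata when they hardly matter and keeps both in 98% of trials at R² = 0.30. Repeat runs put the screened model within about 0.3 point (treatment) and 1.3 points (interaction) of always including the strata.

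**Two unranked models.** With the strata as the only candidates and the same screen, rejecting when either Aim 1 model is significant gives about 5 to 5.6% type I error for treatment and about 5 to 8% for the interaction.

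**The case against.** The strongest reply is that the silence is that of a summary. A complete plan is held elsewhere, and stratification factors are an ordinary example of the design features that the Aim 1 initial model is to control for. This stands: for Aim 1 the gap may be one of wording only, and these documents cannot show that the strata will be left out.

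It also stands that the losses are small and in the safe direction. At R² of 0.05 to 0.15, treatment power falls by about 1 to 2 points from above 92%. Nothing in the documents supports an R² as high as 0.30 for two yes/no factors beyond baseline ratings. The Aim 1 covariate-adjusted model recovers most of what is lost wherever the loss is material.

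Three stronger readings are tempting. A reader might infer that omitting the strata inflates false positives; it does the opposite for treatment and leaves the interaction at 5%. A reader might apply the largest power loss to the whole analysis; it applies only to a model without the strata, at the highest assumed R². A reader might hope that adjustment repairs interaction power near 35%; that is a matter of sample size and of how 0.64 is defined.

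What remains is that inclusion is not guaranteed in Aim 1, that no route to it is stated in Aim 2, and that the two Aim 1 models are unranked.

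**Conclusion.** The point holds as a free improvement in specification; it is not a demonstrated flaw. In these documents neither stratification factor is named in any analysis, and no Aim 1 model is designated primary.

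If the strata are prognostic, a model without them is conservative for treatment and gives up about 1 to 3.5 points of treatment power and 1 to 11 points of interaction power over R² of 0.05 to 0.30. This concerns the Aim 1 initial model. It carries to Aim 2 only by analogy, since session-level data, time-varying covariates and missing sessions were not modelled. Aim 3 was not quantified.

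The choice between Aim 1 models matters mainly for the interaction, at about 5 to 8% error instead of 5%. More candidate covariates could raise this. All sizes rest on the assumed R², prevalences, block size and screening rule. If the fuller plan already names the strata and a primary model, its wording need only be carried over.

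**What to change.** State in the plan:

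1. Both stratification factors, as recorded at randomisation, are fixed covariates in every Aim 1 and Aim 2 model.
2. One Aim 1 model is primary, with a covariate list fixed in advance: treatment, task order, both strata, the planned baseline ratings, and gender with treatment by gender where that is tested. Models with outcome-selected covariates are sensitivity analyses.
3. In exploratory Aim 3, the log-rank and Cox analyses are stratified or adjusted by the same two factors.
4. The Aim 1 task-level ratings, taken five minutes before each task on days 39 and 40, and the Aim 2 pre-cue ratings are measured after randomisation, on study medication. Keep them only as reactivity adjustments, and say that the estimate is then of reactivity beyond any drug effect on pre-task or pre-cue levels.

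The cost is wording, settled before unblinding, and 2 degrees of freedom per Aim 1 or Aim 2 model. If the strata turn out irrelevant, about half a point of power or less is lost. No new data, participants or allocation list are needed.

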**A.7. Conclusions.** OUDs are increasing at alarming rates in women. Stress and dysregulation in biologic stress response systems appear to play an important role in drug use and the connection between stress and drug use may be particularly important for women. Alterations in CRF, the HPA axis and noradrenergic system are important in the pathophysiology of OUDs and there is evidence that agents that decrease noradrenergic activity may help to prevent relapse and stress reactivity in individuals with OUDs, but gender differences in these effects have not been systematically explored. The primary objective of this study is to explore gender differences in the impact of an alpha-2 agonist, lofexidine, on the relationship between stress, craving and drug use in individuals with OUDs.

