**C.1.c.** Stress Induction Procedures and Neuroendocrine/Physiologic Measurement. [name] has conducted a number of human laboratory studies involving stress induction and drug cue exposure in alcohol, cocaine and nicotine dependence ([name] et al., 2009; Moran et al., 2014; Hartwell et al., 2011; [name] et al., 2006). Of direct relevance, [name] and colleagues completed a pilot study involving a human laboratory stress task in 39 (N=19 women; 20 men) individuals with OUD. Subjects were randomly assigned to either the Trier Social Stress Test (TSST; n=19) or no-stress control (no stress; n=20) followed by opioid cue exposure. Distress tolerance, Inventory of Drug Taking Situations and Time-line Follow-back were completed at baseline. Self-reported visual analog scale ratings of stress and craving, as well as heart rate and salivary cortisol were assessed immediately before and at multiple time points for 60 minutes following the TSST/drug cue exposure. Individuals were followed for one month after the laboratory session to assess opioid use (Time-line Follow-Back) and daily stress. Significant group (TSST vs. no stress) differences emerged in self-reported stress [F(1,35)=41.77, p<.001], anger [F(1,35)=13.00, p<.001], sadness [F(1,35)=4.78, p<.05], cortisol and heart rate

(HR) [F(1,35)=5.28, p<.05], with the TSST group exhibiting more reactivity. Women demonstrated significantly greater self-reported stress [F(1,35)=11.24, p<.01], (Figure 1); however, they exhibited significantly less cortisol response following the TSST as compared to men. Data (Figure 2) are shown as log 10 transformed model-

[figure not shown]

Figure 1: Stress Response

Figure 2: Cortisol Response

based means and standard errors adjusted for baseline cortisol. Of interest, women also exhibited a significantly protracted HR response following the TSST compared to men; it had not returned to baseline by the end of the

[figure not shown]

Figure 3: Heart Rate Response

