reactivity and drug craving, collect data on drug use and withdrawal symptoms, validate abstinence, and measure/encourage medication adherence. The Cue Reactivity Ecological Momentary Assessment (CREMA) paradigm was modified to assess cue- and stress-related nicotine craving (Wray et al., 2015). Over 80% of CREMA sessions were successfully completed (Tomko et al., 2017), supporting the feasibility of remote collection of this type of data. We also capitalized on the capabilities of the REDCap data system to remotely collect self-report of drug use and video confirmation of medication adherence (Tomko et al., in press). In a smoking cessation trial, there was high compliance with video (73.8%) and self-report (74.8%) completion. All

participants agreed that the surveys and videos were easy to use, and the majority of participants preferred the REDCap assessments to traditional, paper measures. In an ongoing pharmacotherapy trial for cannabis use disorder (UG3DA04323), we have observed high compliance with video uploads for medication adherence, with a median of 80% of medication doses verified.

- **C.2.** Research Design and Methods. This project is a double-blind, placebo-controlled trial to assess gender differences in the impact of lofexidine, an alpha-2 agonist, on stress-related opioid craving in men and women with OUD on stable buprenorphine or methadone maintenance. Following this period, participants will be randomized to receive either lofexidine or placebo for a 5-week period during which cue reactivity ecological momentary assessment (CREMA) will be used to assess stress levels, craving and drug use and video confirmation of medication adherence will be employed. Naturalistically collected stress and drug cue reactivity data will be complemented by administration of a validated laboratory stress (the Trier Social Stress Task) and drug cue exposure procedure at the end of the 5-week treatment period while participants are still taking study medications. A schematic of study procedures is shown below.
- **C.2.a. Participants.** A total of 136 participants (68 men and 68 women) with OUD who have been on a stable dose of buprenorphine or methadone for at least 2 weeks, aged 18 to 65 years of age, will be recruited over a 54-

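### Gender is the effect modifier of interest but is neither a randomisation stratum nor a prespecified term in the initial Aim 1 models for Hypotheses 1 and 2; the cost is precision for subjective stress, not validity

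*Combined protocol and SAP*

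**What the plan says.** **Objective.** Sections A.6 and A.7 both state: "The primary objective of this study is to explore gender differences in the impact of an alpha-2 agonist, lofexidine".

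**Recruitment.** C.2.a sets the gender totals: "A total of 136 participants (68 men and 68 women) with OUD".

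**Allocation.** The randomisation text in C.2.c.5, Phase 1, item d, names two factors: "Randomization will be stratified on presence/absence of other substance use as well as the presence/absence of significant childhood trauma (ACE>4".

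**Sample size.** Power and Sample Size is framed on the interaction, with an effect of "Cohen's d=0.64 for the sex x treatment interaction on craving response". It assumes equal gender-by-arm cells, "39 participants randomized to each female and males across active lofexidine and placebo groups", which "would provide 80% power with a type 1 error rate of 5% to detect the treatment x sex interaction".

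**Models.** C.2.d, Aim 1, describes three layers:
- The initial models: "Initial models will control for study design aspects such as order (stressor or cue first), treatment assignment, and baseline craving and stress (task level".
- Covariate-adjusted models, which add baseline characteristics found to correlate with outcome or to be significant effect modifiers.
- The models for the gender question, which add a gender indicator and its interaction with treatment. Gender is named only here.

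**Pilot.** C.1.c reports, for 39 people with opioid use disorder: "Women demonstrated significantly greater self-reported stress [F(1,35)=11.24, p<.01".

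**The concern.** Fixing 68 women and 68 men fixes the gender totals only. It does not fix how women, or men, divide between lofexidine and placebo. The plan therefore balances two factors that are not its main question and leaves the one that is to chance.

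For Hypotheses 1 and 2 the unadjusted arm comparison absorbs whatever gender imbalance arises, and any variation due to gender stays in the residual. The sponsor's own pilot gives reason to expect such variation in self-reported stress. A covariate known in advance to be central to the question should not depend on a selection rule applied to the outcome data.

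**Working it through.** **1. The plan's own figure.** With two-sided 5% and 80% power, a plain two-group comparison at d = 0.64 needs 2 × (1.96 + 0.8416)² / 0.64² = 38.3, so 39 per group. That reproduces the 39, but as a group size. If 0.64 is the difference of differences, each cell needs 4 × (1.96 + 0.8416)² / 0.64² = 76.7, so 77. The plan also randomises 136, below the 156 it sets out to inflate. These are separate and larger problems that gender stratification does not touch. The steps below use the 136 actually planned.

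**2. How far the cells can drift.** Take 68 women and 68 men, 68 per arm, and no gender stratum. The number of women on lofexidine is then hypergeometric with mean 34 and SD 2.9 (95% range 28 to 40). A 28:40 split or worse has probability 0.059. Under simple randomisation the SD is 4.1 and that probability is 0.18.

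**3. Effect on the interaction.** The standard error, in SD units, is √(sum of 1/n over the four cells).
- 34 in every cell: √(4/34) = 0.343. Power for 0.64 is Φ(0.64/0.343 − 1.96) = 46.2%.
- A 40/28 split: √(2/40 + 2/28) = 0.348, power 45.1%.
- Averaged over all possible splits: 46.0% with arms fixed at 68, 45.7% under simple randomisation.
- At 102 completers (136 × 0.75): 36.5% balanced, against 36.2% and 35.9%.

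The average loss is under one percentage point.

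**4. Strength of gender in the pilot (self-reported stress).**
- Partial eta-squared = 11.24 / (11.24 + 35) = 0.243.
- Standardised difference with 19 women and 20 men = √(11.24 × (1/19 + 1/20)) = 1.07. Table 1 of the protocol gives 18 women and 21 men, which changes this only to 1.08.

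**5. Shift from a chance imbalance in an unadjusted stress comparison.**
- 40:28 split: (40 − 28)/68 × 1.07 = 0.19 SD.
- Imbalance of one SD: (2 × 2.93)/68 × 1.07 = 0.09 SD.

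The standard error of the arm contrast with 51 completers per arm is √(2/51) = 0.20 SD, so even the 40:28 case is about one standard error.

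**6. Gain from putting gender in the Hypothesis 1 and 2 models.** The power column uses an illustrative treatment effect of d = 0.5, with 51 completers per arm.

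| Share of residual variance due to gender | Equivalent gain in participants, 1/(1 − share) | Power |
|---|---|---|
| 0 | none | 71.4% |
| 0.05 (assumed) | 5% | about 74% |
| 0.10 (assumed) | 11% | about 76% |
| 0.243 (pilot, stress) | 32% | 82.7% |

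The documents give no gender effect on craving in the pilot, so no row can be assigned to craving.

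**7. Would the data-driven rule find gender?** With 102 completers the standard error of a gender difference is 2/√102 = 0.198.
- At the pilot size, z = 1.07/0.198 = 5.4, so selection is near certain.
- At a 5% share, the difference is 2√(0.05/0.95) = 0.46 and z = 2.3. A 5% significance screen would then admit gender about 64% of the time. The plan states no threshold, so the 5% is an assumption.

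**The case against.** The strongest reply is that the plan already provides for gender. The covariate-adjusted models admit characteristics that correlate with outcome, relevant interactions are to be assessed in all models, and the Hypothesis 3 model carries gender and its interaction outright. If gender is as strong as the pilot suggests, the rule will pick it up. If it is weak, little is lost by missing it. This largely stands. A reader might infer that gender is absent from the Aim 1 analysis, or that a strong predictor is bound to stay in the error. The text does not support either. What remains is that adjustment depends on an outcome-driven rule with no stated threshold, so which Hypothesis 1 and 2 result is the adjusted one is not fixed in advance.

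Second, the pilot can be over-read. It had 19 participants on the TSST and 20 on no stress. An error df of 35 (39 − 4) fits a gender main effect pooled over both conditions, not a response specific to the TSST. No baseline adjustment is stated for that rating, whereas the trial models adjust for task-level baseline, which may absorb much of a difference in level. This stands too, and makes 24% an upper bound for stress alone.

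Third, the list of terms in the initial models opens with wording that makes it illustrative, and C.2.d refers to a complete plan in the Biostatistics Resource Core that was not available. Gender may be specified there. If so, C.2.d should say so.

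Fourth, stratifying now helps only those not yet allocated. The protocol is marked V20, 7.25.23, and does not state enrolment status.

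**Conclusion.** The point holds as a matter of prespecification and efficiency. Gender is the effect modifier the trial exists to study, yet it is not a stratum and is not named in the initial Hypothesis 1 and 2 models.

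Two stronger conclusions should not be drawn. A reader might infer that the treatment comparison is biased. It is not: randomisation keeps the tests valid, and the unadjusted standard error already includes chance gender imbalance, so the shift in step 5 and the residual variance in step 6 are one cost, not two. A reader might also infer that the gender-by-treatment test is compromised. The average loss there is under one point of power.

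The benefit lies in the Hypothesis 1 and 2 subjective-stress comparison: at most about 24% of residual variance, perhaps 5% to 10% after baseline adjustment, and unknown for craving. The power figures assume two-sided 5% tests, unit SD, the normal approximation and 25% attrition spread evenly over cells. The 24% assumes the pilot effect carries over in full, and the 5% to 10% is an assumed range.

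**What to change.** 1. In C.2.d, Aim 1, name participant gender as a fixed main effect in every model for Hypotheses 1 and 2, initial and covariate-adjusted, so that it no longer depends on outcome correlation. This takes one sentence, uses data already collected, and can be done at any time before unblinding.

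2. In the randomisation text of C.2.c.5, Phase 1, item d, add gender as a stratification factor for any remaining randomisations. The Investigational Drug Service would need an updated list. The two existing factors give four strata, and gender makes 2 × 2 × 2 = 8, averaging 136/8 = 17 participants over the whole trial, with slightly more incomplete blocks. Participants already allocated are unaffected. If few randomisations remain, the first change delivers nearly all of the benefit.
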